5.3.2 Safety Populations

- **PSMA-11 Safety Analysis Set:** All patients who received a dose of ⁶⁸Ga-PSMA-11. This includes screened patients that are not enrolled (i.e., not randomized). Patients enrolled will be included in the treatment arm to which they were randomized.

- **FAS Safety Analysis Set:** The subset of patients in the FAS who received at least one dose of randomized treatment. Patients will be included in the treatment arm corresponding to the actual treatment received.

5.3.3 Sub-study Populations

- **PSMA-11 Sub-study Analysis Set:** All patients who received a dose of ⁶⁸Ga-PSMA-11 in the sub-study conducted at sites in Germany. This includes screen failure patients who are not enrolled in the sub-study.
- **Sub-study Safety Analysis Set:** All patients who received at least one dose of the investigational treatment (¹⁷⁷Lu-PSMA-617+BSC/BSoC) in the sub-study conducted at sites in Germany.

5.4 Subgroup Definitions

The following subgroups are defined for the study:

1. Stratification Factor (based on CRF data) – Inclusion of NAADs (e.g., enzalutamide, abiraterone, or apalutamide) as part of assigned BSC/BSoC treatment at start of study (Yes vs. No). See Section 5.6 for derivation.
2. Number of cycles in the ¹⁷⁷Lu-PSMA-617 + BSC/BSoC treatment arm (≤ 4 cycles vs. 5-6 cycles).
3. Stratification factor (based on CRF data) – Baseline LDH (≤ 260 IU/L vs. > 260 IU/L). See Section 5.6 for derivation.
4. Stratification factor (based on CRF data) – Presence of liver metastases at baseline (Yes vs. No). See Section 5.6 for derivation.
5. Stratification factor (based on CRF data) – ECOG score at baseline (0 or 1 vs. 2). See section for derivation.
6. Age (< 65 years vs. ≥ 65 years)
7. Race (White vs. Black or African American vs. Asian vs. Other (includes “Native Hawaiian or Other Pacific Islander”, “American Indian or Alaska Native” or more than one race reported))

5.4.1 Analyses on subgroups

All subgroup analyses are to be considered exploratory and descriptive; p-values presented with efficacy results will be treated as nominal.

Efficacy analyses The alternate primary endpoints, rPFS and OS, will be summarized and analyzed by the following subgroups (defined in Section 5.4) to assess the consistency of treatment effect provided either or both primary endpoints are statistically significant:

- Inclusion of NAADs as part of assigned BSC/BSoC treatment at start of study
- Baseline LDH
- Presence of liver metastases at baseline
- ECOG score at baseline
- Age
- Race

No formal statistical test of hypotheses will be performed for the subgroups. For each subgroup, a stratified cox regression model will be used to estimate the treatment effect

stratifying for the randomization factors from IRT. When one of the stratification factors is the subgroup of interest, that factor will be excluded from the stratified model. The model will include three terms: treatment, subgroup (e.g. ECOG score at baseline) and treatment by subgroup interaction. The HR and associated confidence interval for each subgroup will be estimated from the model. Kaplan-Meier estimates as described for the alternate primary endpoints (Section 8.2.1) will also be provided excluding the log-rank test p-value. Subgroup analyses of rPFS and OS will be presented graphically using forest plots.

The efficacy analyses in subgroups will only be performed if at least 10% of patients or 10 patients are present in each class.

Key safety analyses of exposure, adverse events and clinical laboratory values will be performed as described in Section 9, on the FAS and PSMA-11 safety analysis sets (defined in Section 5.3.2) in the following subgroups (defined in Section 5.4):

- Inclusion of NAADs as part of assigned BSC/BSoC treatment at start of study (FAS Safety Analysis Set only)
- Number of cycles received in the ¹⁷⁷Lu-PSMA-617 + BSC/BSoC treatment arm (FAS Safety Analysis Set only)
- ECOG score at baseline (FAS Safety Analysis Set only)
- Age (FAS Safety Analysis Set and PSMA-11 Safety Analysis Set)
- Race (FAS Safety Analysis Set and PSMA-11 Safety Analysis Set)

The objective for carrying out these subgroup analyses is to identify potential safety issues that may be limited to a subgroup of patients, or safety issues that are more commonly observed in a subgroup of patients. Summary tables will only be performed if at least 10% of patients or 10 patients are present in each subgroup.

The results of the efficacy and safety subgroup analyses will be presented in separate tables and figures from study arm results.

Separate listings will not be created for subgroups.

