If the patient meets all of the criteria above, and agrees to continue with additional treatment of ¹⁷⁷Lu-PSMA-617, the investigator may administer a further 2 cycles. A maximum of 6 cycles of radioligand therapy is allowed. If the patient does not meet any of the criteria or does not agree to additional ¹⁷⁷Lu-PSMA-617 treatment, then no additional doses of ¹⁷⁷Lu-PSMA-617 will be administered after Cycle 4. After the last cycle of ¹⁷⁷Lu-PSMA-617, patients can continue best supportive/best standard of care alone.

Best supportive/best standard of care for each patient will be selected at the discretion of the patient's physician, prior to randomization and will be administered per the physician's orders and continued until the patient comes off the treatment part of the study and enters the long-term follow-up stage.

A patient may choose to discontinue randomized treatment part of the study at any time.

Before final analysis of alternate primary endpoint OS:

If a patient chooses only to discontinue from the randomized treatment in the study for a reason other than radiographic progression, the patient will be asked to confirm if they consent to continue to be followed for long-term safety, rPFS, and survival follow-up. The patient will continue to be followed for long-term follow-up unless they specifically withdraw consent from long-term follow-up of the study. An End of Treatment (EOT) visit should occur once a patient discontinues randomised treatment for any reason (patient or investigator decision, going on to long-term follow-up, etc.).

The EOT visit should occur approximately 30 days from the last dose of ¹⁷⁷Lu-PSMA-617 or the date of the best supportive/best standard of care end of treatment decision (whichever occurs later), but before the initiation of subsequent anti-cancer treatment, outside of what is allowed on study.

If a patient discontinues randomized treatment for any reason other than radiographic progression, they will be asked for permission to continue collecting radiographic images (bone scans and CT scans and/or MRIs) for the purpose of continuing to assess rPFS.

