5.1.4 Management of toxicity adverse events: dosing delays and modification

Within the first few days of treatment the most common adverse events (AEs) are general fatigue and an increase in bone pain. Symptomatic hematologic toxicity may occur but is not common.

Every effort should be made to keep the treatment cycle of 6 weeks (\pm 1 week) at the prescribed doses. Physical exams, assessment of toxicities, along with hematology and chemistry results must all be assessed prior to dosing with ^{177}Lu -PSMA-617. At the discretion of the investigator, a dose of ^{177}Lu -PSMA-617 may be delayed or reduced. Table 1 provides dose modification recommendations. Only one reduction in administered activity is permitted. If a patient has further toxicity that would require an additional reduction in administered activity, treatment with ^{177}Lu -PSMA-617 must be discontinued. Once a dose is reduced, treatment with ^{177}Lu -PSMA-617 should not be re-escalated.

If a treatment delay due to adverse event or toxicity management persists for >4 weeks, treatment with ^{177}Lu -PSMA-617 must be discontinued. If treatment with ^{177}Lu -PSMA-617 is discontinued due to an AE, abnormal laboratory value, or toxicity, treatment with best supportive/best standard of care may continue at the discretion of the investigator if the patient has not radiographically progressed as measured by PCWG3 criteria.

Table 1 Toxicity management and dose modification recommendations

Event	Grade	Management recommendations
Anemia, leukopenia, or neutropenia: 
 • Hemoglobin <10 g/dL • WBC count $<3.0 \times 10^9/\text{L}$ • ANC $<1.5 \times 10^9/\text{L}$ 	\geq Grade 2	Hold ^{177}Lu -PSMA-617 administration until improvement to Grade 1 or baseline. Manage as deemed appropriate by investigator. The use of growth factors is permitted but should be discontinued once the AE resolves to Grade 1 or baseline. Checking hematinic levels (iron, B12, and folate) and providing supplementation is advocated. Transfusions may be given as clinically indicated for anemia.
Thrombocytopenia (platelet count of $<75 \times 10^9/\text{L}$)	\geq Grade 2	Hold ^{177}Lu -PSMA-617 administration until improvement to Grade 1 or baseline. Transfusions may be given as clinically indicated for thrombocytopenia.

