Hematological toxicity (except lymphocytopenia that responds to medical intervention)	Grade 3 or Grade 4	Hold ^{177}Lu -PSMA-617 administration until improvement to Grade 1 or baseline. Reduce ^{177}Lu -PSMA-617 dose by 20% on the next cycle
Serum/plasma creatinine increased $\geq 40\%$ from baseline AND calculated creatinine clearance decreased $>40\%$ from baseline		Reduce ^{177}Lu -PSMA-617 dose by 20% on the next cycle

Table 1 Toxicity management and dose modification recommendations

Event	Grade	Management recommendations
Salivary gland toxicity	≥ Grade 2	Reduce ¹⁷⁷ Lu-PSMA-617 dose by 20% on the next cycle
Non-hematological, clinically significant toxicity not otherwise stated	≥ Grade 2	Hold ¹⁷⁷ Lu-PSMA-617 administration until resolved to Grade 1 or baseline
Electrolyte or metabolic abnormalities that are correctable within a 48 hr period without sequela	≥ Grade 2	Hold ¹⁷⁷ Lu-PSMA-617 administration until resolved to Grade 1 or baseline
Gastrointestinal toxicity (not amenable to medical intervention)	≥ Grade 3	Hold ¹⁷⁷ Lu-PSMA-617 administration until resolved to Grade 2 or baseline Reduce ¹⁷⁷ Lu-PSMA-617 dose by 20% on the next cycle
Fatigue	≥ Grade 3	Hold ¹⁷⁷ Lu-PSMA-617 administration until resolved to Grade 2 or baseline
Pain	≥ Grade 3	Hold ¹⁷⁷ Lu-PSMA-617 administration until resolved to Grade 2 or baseline
Spinal cord compression		Hold ¹⁷⁷ Lu-PSMA-617 administration until the compression has been adequately treated and hematological parameters have returned to Grade 1 or baseline and ECOG performance status has returned to baseline at the time the next cycle administration is due
Fracture in weight bearing bones		Hold ¹⁷⁷ Lu-PSMA-617 administration until fracture is adequately stabilized/treated and hematological parameters have returned to Grade 1 or baseline and ECOG performance status has returned to baseline at the time the next cycle administration is due
AST or ALT >5 × ULN in the absence of liver metastases		Discontinue ¹⁷⁷ Lu-PSMA-617
Renal toxicity	≥ Grade 3	Discontinue ¹⁷⁷ Lu-PSMA-617
Any serious AE that requires drug discontinuation or treatment delay of >4 weeks		Discontinue ¹⁷⁷ Lu-PSMA-617
Any unacceptable toxicity		Discontinue ¹⁷⁷ Lu-PSMA-617

Note: Hematologic parameters (i.e., CBC with differential analysis) will be monitored every week in Cycle 1 only. Cycles 2 to 6, it will be monitored every 2 weeks. After Cycle 6, it will be monitored every 12 weeks.

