3.1 Study Design

This is a Phase 3, open-label, international, randomized study to evaluate the efficacy and safety of ¹⁷⁷LuPSMA-617 in patients with progressive PSMA positive mCRPC, when administered in addition to best supportive/best standard of care (BSC/BSoC) as compared to BSC/BSoC alone (Figure 1).

Figure 1 Diagram of trial design

ECOG = Eastern Cooperative Oncology group; EQ-5D-5L = European Quality of Life (EuroQoL) – 5 Domain 5 Level scale; FACT-P = Functional Assessment of Cancer Therapy – Prostate; mCRPC = metastatic castration-resistant prostate cancer; PSMA+ = prostate-specific membrane antigen positive; RECIST = Response Evaluation Criteria in Solid Tumors

BSC/BSoC includes available care for the eligible patient according to best institutional practice and at the discretion of the investigator. Novel androgen axis drugs [NAADs] (i.e., enzalutamide, abiraterone, or apalutamide) are allowed.

Investigational agents, cytotoxic chemotherapy, immunotherapy, other systemic radio isotopes (e.g. radium-223) or hemi-body radiotherapy treatment may not be administered on study.

At screening, potential subjects will be assessed for eligibility and will undergo a ⁶⁸Ga-PSMA-11 PET/computed tomography (CT) scan to evaluate PSMA positivity. Only patients with PSMA-positive cancer will be randomized in a 2:1 ratio to receive either ¹⁷⁷Lu-PSMA-617 plus BSC/BSoC (investigational arm) or to receive BSC/BSoC only (BSC/BSoC-only arm). Randomization will be stratified by 4 factors (Section 3.2).

Patients randomized to the investigational arm must begin ¹⁷⁷Lu-PSMA-617 dosing within 28 days of randomization. These patients will receive BSC/BSoC and 7.4 GBq ($\pm 10\%$) ¹⁷⁷Lu-PSMA-617 once every 6 weeks (± 1 week) for a maximum of 6 cycles.

After the Cycle 4 dose of ¹⁷⁷Lu-PSMA-617 and prior to Cycle 5 Day 1, the investigator should determine if:

- The patient shows evidence of response (i.e. radiological, Prostate-specific antigen (PSA), clinical benefit) and
- Has signs of residual disease on CT with contrast/MRI or bone scan and
- Has shown good tolerance to the ¹⁷⁷Lu-PSMA-617 treatment.

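### Safety tables by cycles received (≤4 vs 5-6) condition on a post-randomization outcome, so they cannot show whether cycles 5-6 add toxicity

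*SAP*

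**What the plan says.** SAP 5.4 defines a subgroup of the investigational arm by ¹⁷⁷Lu-PSMA-617 cycles, "≤ 4 cycles vs. 5-6 cycles". SAP 5.4.1 applies it to safety: "Key safety analyses of exposure, adverse events and clinical laboratory values will be performed as described in Section 9", with this entry in the list: "Number of cycles received in the ¹⁷⁷Lu-PSMA-617 + BSC/BSoC treatment arm (FAS Safety Analysis Set only". The stated aim of all the safety subgroups is to "identify potential safety issues that may be limited to a subgroup of patients", or that are more common in one.

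The rules that decide who is in which group are these.

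- **Entry to cycle 5** (Protocol 3.1, SAP 3.1). The investigator must find evidence of response and residual disease, and the patient "Has shown good tolerance to the" study drug. The protocol adds: "If the patient meets all of the criteria above, and agrees to continue with additional treatment of" study drug, two more cycles may be given.
- **Earlier stopping** (Protocol 5.1.4). One rule begins "If a treatment delay due to adverse event or toxicity management persists for >4 weeks, treatment with" study drug ends. Table 1 also lists "Any serious AE that requires drug discontinuation or treatment delay of >4 weeks" as a reason to discontinue.
- **Other exits** (Protocol 3.4.5 and 5.5). These include radiographic progression, withdrawal and lack of clinical benefit.

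The measures are crude. SAP 9.2.2 counts patients with at least one event. SAP 9.2.1 lets the window run to 30 days after the last randomized treatment or the day before subsequent anticancer therapy, whichever is first. SAP 9.3 uses the worst on-treatment laboratory value. For this subgroup the SAP gives no landmark, no exposure-adjusted rate and no caution about interpretation.

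**The concern.** The number of cycles received is a result of treatment, not a baseline feature. A patient who had a toxicity in cycles 1-4 that ended ¹⁷⁷Lu-PSMA-617 must be in the ≤4 column. A patient in the 5-6 column had passed a tolerance check before the two extra cycles began. His events from cycles 1-4 are counted as well, but he is there because they were tolerable.

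Exposure works the other way. A patient with six cycles has more time in which to record at least one event, so a crude percentage rises with cycles even if the risk per cycle is constant.

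Safety and tolerability is a stated secondary objective. The prospective phase 2 study cited in Protocol 1.1 gave up to four cycles, and for more than four Protocol 3.4.2 relies on clinical series and a review. A reader will therefore look in these columns for what cycles 5 and 6 add, and may be reassured or alarmed without cause.

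**Working it through.** The documents give no event rate by cycle and no expected share reaching cycle 5, so there is no planned figure to reproduce. All rates below are assumptions. The structure (six cycles, a check after cycle 4, percentage with at least one event) is from the documents. Events are counted only while on ¹⁷⁷Lu-PSMA-617, a simplification of the longer window in the SAP.

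**Step 1. Two extremes, by hand.** Assume an event risk of 10% per cycle, the same for every patient; 10% leave per cycle for other reasons; and 60% meet the other conditions for cycle 5 and agree.

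The chance of a first event in cycles 1-4 is 0.10 × (1 + 0.81 + 0.81² + 0.81³) = 0.2998, where 0.81 = 0.9 × 0.9.

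*Full selection: nobody with an event gets cycle 5.*
- Share reaching cycle 5: 0.81⁴ × 0.6 = 0.258.
- ≤4 group: 0.2998 / (1 − 0.258) = 40.4%.
- 5-6 group, same hazard: 0.10 + 0.9 × 0.9 × 0.10 = 18.1%.
- 5-6 group, doubled hazard (risk per cycle 1 − 0.9² = 0.19): 0.19 + 0.81 × 0.9 × 0.19 = 32.9%.

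The risk is doubled, yet the column reads 32.9% against 40.4%.

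*No selection: events do not affect continuation.*
- Share reaching cycle 5: 0.9⁴ × 0.6 = 0.394, of whom 1 − 0.9⁴ = 34.4% had an event in cycles 1-4.
- ≤4 group: (0.2998 − 0.394 × 0.344) / (1 − 0.394) = 27.1%.
- 5-6 group, same hazard: 1 − 0.6561 × (1 − 0.181) = 46.3%.
- 5-6 group, doubled hazard: 1 − 0.6561 × (1 − 0.329) = 55.9%.

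Here nothing is added in cycles 5-6, yet the column reads 46.3% against 27.1%.

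**Step 2. Between the extremes, by simulation.** The hazard has mean 0.06 per cycle and varies between patients (gamma, shape 1). The event risk per cycle is 1 − exp(−hazard × k), with k = 1 in cycles 1-4 and k as shown in cycles 5-6. In each cycle 12% leave for other reasons, and 30% of event-free patients do not get cycle 5. There are 2,000,000 patients per row. The first column gives the chance that an event stops treatment and the chance that a patient with a prior event is not given cycle 5.

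| Selection | k | ≤4 | 5-6 | Onset in cycles 5-6, among those starting cycle 5 |
|---|---|---|---|---|
| 50% / 80% | 1 | 23.6% | 11.1% | 8.6% |
| 50% / 80% | 2 | 23.5% | 17.9% | 15.7% |
| 50% / 80% | 3 | 23.5% | 23.8% | 21.9% |
| 30% / 60% | 1 | 21.1% | 15.9% | 9.0% |
| 30% / 60% | 2 | 21.1% | 22.4% | 16.6% |
| 10% / 40% | 1 | 17.1% | 22.5% | 9.7% |
| 10% / 40% | 2 | 17.1% | 28.3% | 17.7% |

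At 50% / 80% and k = 2, changing the gamma shape to 0.7 or 2 gives 22.9% vs 16.3% and 24.4% vs 20.1%. The selection inputs decide the sign; the shape does not.

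**Step 3. What the last column shows.** Counting only events that start in cycles 5-6, among patients who started cycle 5, gives 8.6% to 9.7% with no added hazard and 15.7% to 17.7% with a doubled one. The excess shows at each selection setting in the table.

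**The case against.** Several points on the other side are fair.

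- **The 5-6 column need not look safer.** A reader might infer that it will always show fewer events. The documents do not support this. The percentages are crude and exposure is longer, and in the table the reversal for a doubled hazard is gone at 30% / 60%. For frequent low-grade effects that seldom stop treatment, the 5-6 column would tend to look worse.
- **Early stopping need not be mostly for toxicity.** A reader might infer that too. Toxicity is one of several documented reasons and no frequency is given.
- **The table is not said to establish the safety of the optional cycles.** SAP 5.4.1 gives one generic aim for all safety subgroups, and a description of who stopped early, and with which events, keeps some value.
- **Part of the remedy exists.** SAP 9.2.4 (footnote 3) tabulates TEAEs and serious TEAEs by cycle of onset. Fatal events, discontinuations and deaths have their own arm-level tables, and laboratory values are summarized by visit. SAP 5.4.1 calls all subgroup analyses exploratory and descriptive, and leaves cycles received out of the efficacy subgroups.

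The first three points limit the claim, and it is stated here within those limits. The fourth answers it only in part. The onset tables are specified for TEAEs and serious TEAEs only and state no denominator of patients starting each cycle. They also leave the ≤4 vs 5-6 tables as they are. A descriptive label limits inference but does not remove bias from the numbers printed.

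**Conclusion.** The concern holds in a limited form. The ≤4 vs 5-6 safety tables mix selection on response and tolerance with longer exposure. The two biases oppose each other and the documents do not allow their net direction to be predicted, so a lower, equal or higher percentage in the 5-6 column does not tell a reader whether cycles 5-6 add toxicity.

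The structural point rests on the text alone. The sizes rest wholly on assumed rates and show only that misleading results in either direction are plausible. The importance is modest: the tables are descriptive, and no primary, key secondary or alpha-controlled result depends on them.

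**What to change.** In SAP 5.4.1, in place of the whole-period ≤4 vs 5-6 comparison of adverse events and laboratory values:

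1. Give incidence by cycle of onset, with the patients who started that cycle as denominator. Extend the SAP 9.2.4 footnote 3 tables to grade ≥3, fatal and discontinuation TEAEs and to laboratory worsening.
2. Add a landmark table at the Cycle 5 decision. Include patients who received four cycles and are still on study treatment, and compare those who did and did not receive cycle 5. Count only events and laboratory worsening after the landmark, per patient-month. Define the landmark date in the same way for both groups, for example 42 days after the Cycle 4 dose (the cycle length in SAP Section 5), and say how a later Cycle 5 is classed.
3. State beside both tables that patients starting cycle 5 were selected on response and tolerance, that follow-up may end at different times because subsequent therapy closes the window, and that the results are descriptive.

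The cost is table programming. Administration dates are on the CRF and adverse event dates are required fields (SAP 5 and 5.2). The downside is fewer patients and events in the landmark table, and selection that is reduced but not removed. No design element, alpha level or treatment rule changes.

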5.5 Treatment Arms

The following treatment arm labels will be used in the analysis:

- Lu-PSMA-617+BSC/BSoC: ¹⁷⁷Lu-PSMA-617 + Best supportive/best standard of care (investigational treatment arm)
- BSC/BSoC only: Best supportive/best standard of care only (control arm)

5.6 General Variable Definitions

- Time to withdrew consent from ¹⁷⁷Lu-PSMA-617 (days): (Date of withdrew of consent from ¹⁷⁷Lu-PSMA-617 treatment – date of randomization + 1).
- Time to withdrew consent from BSC/BSoC (days): (Date of withdrew of consent from BSC/BSoC – date of randomization + 1).
- Time to withdrew consent from study (days): (Date of withdrew of consent from study – date of randomization + 1).
- Age (years): year of informed consent - year of birth; calculated within clinical database.

- Time since initial prostate cancer diagnosis (years): (Date of informed consent - Date of initial prostate cancer diagnosis)/(365.25). For incomplete dates, see Section 5.2.
- Weight (kg) = weight (lb) * 0.45359237
- Height (cm) = height (in) * 2.54
- BMI (kg/m²) = weight[kg] / (height[m]²) using weight and height at baseline.
- Best % change (where a decrease over time is desirable) = ((smallest post baseline assessment - baseline)/baseline) x 100
- Last taxane therapy treatment-free interval (months): (randomization date - last taxane therapy end date)/(30.4375). For incomplete dates, the see Section 5.2. Taxanes included are those identified as 'Taxane' per WHO Drug ATC Level 4 (e.g. cabazitaxel, docetaxel or paclitaxel).
- Baseline PSA doubling time (months): PSA doubling time will be calculated as natural log of 2 (0.693) divided by the sum of the fixed slope (common to all patients) and the random slope (specific for the patient) of the random coefficient linear model between the natural log of PSA and time of PSA measurement (Svatek et al., 2006). If the PSA doubling time is less than zero (i.e. stable, nonincreasing, or decreasing PSA levels as defined by a negative slope from the random coefficient linear model), the PSA doubling time is set to 0. PSA is collected at screening visit and for the most recent 2 PSA measurements available prior to screening. Calculations will be performed only for subjects with (1) all 3 PSA values with each value ≥ 0.2 ng/mL and (2) for which the interval between the first and last PSA values are ≥ 8 weeks but ≤ 12 months as stated in PCWG3 guidelines (Scher et al., 2016; Pound et al., 1999).

For interpretation of PSA doubling time it should be noted that PCWG3 guidelines state the calculation should be based on the most recent PSA values during androgen deprivation therapy, and that 3 PSA values ≥ 0.2 ng/mL should be consecutive. These additional criteria will not be applied since the information is not available.

- Randomized Treatment (i.e. ¹⁷⁷Lu-PSMA-617 and BSC/BSoC) Exposure Variables:

Average duration of randomized treatment cycles (months) = mean across cycles of (date of dosing for cycle n+1 - date of dosing for cycle n)/30.4375, where n=1 to total number of cycles minus 1.

Duration of exposure (months) = (Date of last exposure to randomized treatment - Reference date + 1)/30.4375. Date of first administration to randomized treatment and date of last exposure to randomized treatment are defined in Section 5.

For duration of exposure to ¹⁷⁷Lu-PSMA-617, the date of last exposure is the date of last exposure to ¹⁷⁷Lu-PSMA-617 and the reference date is the date of first administration of ¹⁷⁷Lu-PSMA-617.

For duration of exposure to BSC/BSoC, the date of last exposure is the date of last exposure to BSC/BSoC and the reference date is the date of first administration of BSC/BSoC (i.e. date of C1D1).

For duration of exposure to a NAAD as study BSC/BSoC, the date of last exposure is the date of last exposure to a NAAD as study BSC/BSoC and the reference date is the date of first administration of a NAAD as study BSC/BSoC.

Dose intensity of ¹⁷⁷Lu-PSMA-617

Dose intensity overall (GBq/month) = (actual total dose of ¹⁷⁷Lu-PSMA-617 during the study) / (actual duration of the study (months)) Note: The duration of the last cycle will be set to 6 weeks (or ~ 1.37 months = 42 /30.4375).

Planned dose intensity overall (GBq/month) = (planned total dose of ¹⁷⁷Lu-PSMA-617 during the study) / (planned duration of the study (months))

Relative dose intensity overall (%) = (dose intensity overall) / (planned dose intensity overall)

Dose intensity of ¹⁷⁷Lu-PSMA-617 per cycle

Dose intensity per cycle (GBq/cycle) = (actual total dose of ¹⁷⁷Lu-PSMA-617 during the cycle)

Planned dose intensity per cycle (GBq/cycle) = (planned total dose of ¹⁷⁷Lu-PSMA-617 during the cycle)

Relative dose intensity per cycle (%) = (dose intensity per cycle) / (planned dose intensity per cycle)

Randomization Stratification Factors based on CRF data

Stratification factor (based on CRF data) – Baseline LDH (≤ 260 IU/L vs. > 260 IU/L) is defined as the latest LDH value on or before the date of randomization as collected on the laboratory CRF page.

Stratification factor (based on CRF data) - Presence of liver metastases at baseline (Yes vs. No) is defined as at least one target and/or non-target liver lesion on or before the date of randomization and/or within 28 days of start of randomized treatment as captured on either the target or non-target lesion CRF pages.

Stratification factor (based on CRF data) – ECOG score at baseline (0 or 1 vs. 2) is defined as the ECOG score captured on the Enrollment CRF page.

Stratification Factor (based on CRF data) – Inclusion of NAADs (e.g., enzalutamide, abiraterone, or apalutamide) as part of assigned BSC/BSoC treatment at start of study (Yes vs. No) is defined as having a NAAD indicated as study BSC/BSoC (see Section 5) on or before the date of C1D1.

6. Study Patients

